2.3 Secondary Objective(s) and Endpoint(s)

Secondary Objective	Endpoint(s)	Time Frame
1. To determine whether the percent change from baseline in $SUV_{max-ave}$ on PSMA PET is associated with time-to-event endpoints including PSA progression-free survival by Prostate Cancer Clinical Trials Working Group 3 (PCWG3) ²⁶ criteria and overall survival.	Association between percent change from baseline in $SUV_{max-ave}$ on PSMA PET with time-to-event endpoints including PSA progression-free survival by PCWG3 criteria and overall survival.	Baseline to time of progression Baseline to time of death
2. To determine whether the percent change from baseline in SUV_{max} on PSMA PET is associated with objective response by Response Evaluation Criteria in Solid Tumors (RECIST) version 1.1 ²⁷ on a per-lesion basis among measurable soft tissue lesions present at baseline	Association between percent change from baseline in SUV_{max} on PSMA PET with objective response by RECIST 1.1 on a per-lesion basis among measurable soft tissue lesions present at baseline.	Baseline to time of objective response

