2.4 Exploratory (Correlative) Objectives

Exploratory Objective
1. To descriptively characterize the histologic, transcriptional, and genomic features of PSMA low/negative lesions among patients who undergo paired optional metastatic tumor biopsy.
2. To descriptively characterize the relationship between $SUV_{max-ave}$ on baseline Ga-PSMA PET with optional baseline FDG-PET.
3. To determine whether heterogeneity of PSMA expression on baseline Ga-PSMA PET is associated with overall survival.
4. To descriptively characterize the patterns of PSMA expression at the time of disease progression among patients who undergo optional PSMA PET.
5. To determine whether the percent change from baseline in PSMA PET is associated with PSA50 response among subgroups of patients defined by treatment modality received, including AR targeting treatment, PSMA-targeting radioligand therapy, cytotoxic chemotherapy, and immunotherapy.

3 Study Design

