3.1 Characteristics

This is a single site phase 2 prospective imaging study evaluating the utility of Ga-PSMA PET to detect treatment response in patients with metastatic castration resistant prostate cancer. There are two sub-cohorts:

- Sub-cohort A1: Patients with castration-resistant prostate cancer *planning* to start a new line of systemic therapy will be enrolled and undergo a baseline pre-treatment ⁶⁸Ga-PSMA-11 PET scan. Patients will then be monitored for treatment response and undergo a repeat ⁶⁸Ga-PSMA-11 PET scan 16 weeks (+/- 8 weeks) after the start of systemic therapy. (*Note: Patients in sub-cohort A1 who initiate systemic therapy during the screening period/prior to study enrollment may be re-consented to transition to sub-cohort A2.*)
- Sub-cohort A2: Patients with castration-resistant prostate cancer *currently* on systemic therapy will be enrolled if a baseline pre-treatment ⁶⁸Ga-PSMA-11 PET scan was performed within 12 weeks prior to the start of systemic therapy, and the on-treatment PSMA PET can be performed within 16 weeks (+/- 8 weeks) after the start of systemic therapy. Patients will then be monitored for treatment response and undergo a repeat ⁶⁸Ga-PSMA-11 PET scan 16 weeks (+/- 8 weeks) after the start of systemic therapy.

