3.3.1 Inclusion Criteria

1. Sub-cohort A1: Patients must have baseline evaluations performed within 12 weeks prior to the start of systemic therapy. (*Note: Patients in sub-cohort A1 who initiate systemic therapy during the screening period/prior to study enrollment may be re-consented to transition to sub-cohort A2.*)
2. Sub-cohort A2: Patients must meet **all** the following requirements:

- Have had a baseline pre-treatment 68Ga-PSMA-11 PET scan and PSA measurement performed within 12 weeks prior to the start of current systemic therapy.
- Able to have an on-treatment 68Ga-PSMA-11 PET and a PSA measurement within 16 weeks (+/- 8 weeks) after the start of current systemic therapy.

Note: The screening period for sub-cohort A2 is within 24 weeks after the patient started their current systemic therapy.

3. Patients must have progressive castration resistant prostate cancer, according to PCWG3 criteria.
4. Patients must have planned initiation of systemic treatment (sub-cohort A1), or ongoing systemic treatment (sub-cohort A2) for castration resistant prostate cancer within 12 weeks of baseline Ga-PSMA PET.
5. Patients must have at least one metastatic lesion with PSMA uptake at or above the blood pool on their baseline PSMA PET scan.
6. The patient must be able and willing to comply with study procedures and provide signed and dated informed consent.
7. Patient must have an Eastern Cooperative Oncology Group (ECOG) Performance Status of 0 or 1.
8. Patient must be Aged 18 years or older at the time of study entry
9. Patients who undergo optional metastatic tumor biopsy following completion of baseline Ga-PSMA PET (sub-cohort A1) must additionally meet all of the following criteria:
 - Presence of one or more metastases by standard radiographic scans that is safely accessible to tumor biopsy in the judgment of treating clinician and/or Interventional Radiology.
 - No history of radiation therapy to the target metastatic lesion selected for tumor biopsy
 - No contra-indication to biopsy including uncontrolled bleeding diathesis.
 - Platelets >75,000/ μ L and PT or INR and a PTT < 1.5 times the institutional ULN within 14 days prior to biopsy

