5.3 Schedule of Procedures and Assessments

5.3.1 Screening Assessments

The screening procedures and assessments must be completed within 12 weeks prior to the start of planned systemic therapy (sub-cohort A1) or within 24 weeks after the start of current systemic therapy (sub-cohort A2). *(Note: Patients in sub-cohort A1 who initiate systemic therapy during the screening period/prior to study enrollment may be re-consented to transition to sub-cohort A2.)*

- Baseline conditions
- Concomitant medications
- Demographic information (e.g. age, race, height, weight, and body mass index)
- ECOG or Karnofsky Performance status
- Laboratory procedures
 - Prostate-specific antigen
 - Complete blood count + differential
 - Lactate dehydrogenase
 - Liver function tests including AST, ALT, total bilirubin, and alkaline phosphatase

Additional screening assessments for sub-cohort A1:

- Baseline ^{68}Ga -PSMA-11 PET scan will be performed and reviewed to confirm the presence of at least one metastatic lesion with PSMA uptake at or above that of the blood pool. A ^{68}Ga -PSMA-11 PET scan performed prior to study entry may serve as the baseline PSMA PET scan if within 12 weeks of the start of systemic therapy.
- Cross-sectional imaging of the chest/abdomen/pelvis (CT or MRI; with IV contrast if medically permissible) within 12 weeks of baseline ^{68}Ga -PSMA-11 PET scan (including the same day as baseline PET). Cross-sectional imaging performed prior to study entry may serve as baseline imaging if within 12 weeks of the start of systemic therapy.

Additional screening assessments for sub-cohort A2:

- Baseline ^{68}Ga -PSMA-11 PET scan performed within 12 weeks prior to start of current systemic therapy will be reviewed to confirm the presence of at least one metastatic lesion with PSMA uptake at or above that of the blood pool
- Cross-sectional imaging of the chest/abdomen/pelvis (CT or MRI; with IV contrast if medically permissible) performed within 12 weeks of baseline ^{68}Ga -PSMA-11 PET scan (including the same day as baseline PET) will be reviewed

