5.3.5 Initiation of Systemic Therapy

- Sub-cohort A1: Patients will subsequently initiate systemic treatment for castration resistant prostate cancer. Choice of therapy will be per discretion of the treating physician. Response monitoring with respect to serum PSA and conventional imaging will occur per standard of care and provider discretion. A minimum of three serum PSA values are required including at baseline within 12 weeks prior to initiation of systemic treatment, at 8 weeks (+/- 4 weeks), and at 16 weeks (+/- 8 weeks) from start of systemic therapy.
- Sub-cohort A2: Patients must be currently receiving systemic treatment for castration resistant prostate cancer, initiated within 12 weeks after their baseline 68Ga-PSMA -11 PET scan. Choice of therapy will be per discretion of the treating physician. Response monitoring with respect to serum PSA and conventional imaging will occur per standard of care and provider discretion. A minimum of two serum PSA values are required including at baseline within 12 weeks prior to initiation of systemic treatment and at 16 weeks (+/- 8 weeks) from start of systemic therapy.

5.3.6 Follow up ⁶⁸Ga-PSMA-11 PET (16 weeks +/- 8 weeks from date of systemic treatment initiation)

Patients will undergo repeat ⁶⁸Ga-PSMA-11 PET after 16 weeks (+/- 8 weeks) from date of initiation of systemic treatment.

The specific time frame for imaging will depend on the treatment modality administered, and will be standardized as follows:

- Androgen Receptor (AR) targeted therapy (20 weeks +/- 4 weeks)
- PSMA-targeting radioligand therapy (12 weeks +/- 4 weeks)
- Cytotoxic chemotherapy (12 weeks +/- 4 weeks)
- Immunotherapy (12 weeks +/- 4 weeks)

Patients with a negative baseline PSMA PET scan (i.e. no metastatic lesion with PSMA uptake at or above that of the blood pool) will not be eligible for the follow up PSMA PET.

Patients who underwent PET/CT at baseline should have same imaging modality performed during follow-up, and likewise patients who underwent PET/MR at baseline should have same imaging modality performed for follow up PSMA PET imaging.

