7.4.3 Secondary Analysis (or Analysis of Secondary Endpoints)

The study cohort will be dichotomized by the median with respect to percent change from baseline in $SUV_{max,ave}$ on PSMA PET. The time-to-event variables including PSA progression-free defined by PCWG3, and overall survival will be compared between dichotomized subgroups using the log-rank test. Kaplan-Meier product limit method will be used to estimate median survival in each subgroup.

Amongst the subset of measurable soft tissue lesions by RECIST 1.1 criteria, on a per-lesion basis, the mean percent change from baseline in SUV_{max} on PSMA PET will be compared between responding lesions by RECIST 1.1 criteria vs. those without response, using Mann-Whitney test.

PSMA negative lesions will be defined as those with SUV values below the mediastinal blood pool. Low positive lesions will be defined as those with SUV_{max} values above the blood pool, but below background liver uptake. Intermediate positive lesions are those defined by SUV_{max} values above background liver, but below parotid gland uptake. High positive lesions are those with SUV_{max} values above that of parotid gland. The histologic, genomic and transcriptional features of each subgroup of PSMA lesion category that has matching tumor tissue will be descriptively reported with particular emphasis on the low and negative PSMA lesions that have paired tumor tissue available.

The median and range for inter-tumoral SUV_{max} across metastatic lesions within individual patients will be descriptively reported, to assess for heterogeneity of PSMA uptake. The cohort will be dichotomized above and below median range of SUV_{max} values to define low and high heterogeneity subgroups. Overall survival from date of onset of mCRPC will be compared between high vs. low heterogeneity subgroups.

Analysis of the correlation between SUV_{max} PSMA and FDG PET will be performed on a per-lesion basis amongst the subset of patients who have paired evaluable imaging using Pearson r correlation coefficient.

Patterns of PSMA expression at the time of progression by PCWG3 criteria will be descriptively characterized.

Comparison of mean percent change from baseline in $SUV_{max,ave}$ in PSA50 responders vs. non-responders will be performed in pre-specified subgroups based on modality of systemic

treatment, including AR targeted therapy, PSMA-directed radioligand therapy, cytotoxic chemotherapy, and immunotherapy.

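### Overall survival by PSMA heterogeneity is counted from mCRPC onset, although patients come under observation only later and no delayed entry is stated

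*Combined protocol and SAP*

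**What the plan says.** - Section 2.4, exploratory objective 3: "To determine whether heterogeneity of PSMA expression on baseline Ga-PSMA PET is associated with overall survival". The exposure is thus read on the baseline scan.
- Section 7.4.3 splits the cohort at the median range of SUVmax and then states: "Overall survival from date of onset of mCRPC will be compared between high vs. low heterogeneity subgroups". It names no test for this comparison and says nothing of delayed entry or adjustment for time since onset. The log-rank test and Kaplan-Meier method in that section are named for the other survival analysis.
- Section 3.3.1 requires progressive castration-resistant disease and sets no upper limit on time since onset. Section 3.1 admits patients starting any new line of therapy.
- Section 2.3 gives the secondary survival objective a different time frame: "Baseline to time of death". No reason is given for using two origins.
- The baseline PET can itself precede enrolment. For sub-cohort A1, Section 5.3.1 allows that a "scan performed prior to study entry may serve as the baseline PSMA PET scan if within 12 weeks" of the start of therapy. For sub-cohort A2, Section 3.3.1 says: "The screening period for sub-cohort A2 is within 24 weeks after the patient started their current systemic therapy".

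**The concern.** A patient who died between mCRPC onset and study entry cannot be in the dataset. On a clock that starts at onset, each enrolled patient therefore carries a stretch of time in which death was impossible by selection. Unless risk sets open at entry, the analysis treats that stretch as observed survival. This is left truncation.

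The comparison is the plan's test of an idea raised in Section 1.5, that low or heterogeneous expression may carry a poor prognosis. At stake are the reported medians, the size of the hazard ratio and, if disease duration before the scan differs between the groups, its direction.

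**Working it through.** **The plan's own figures.** The plan gives no power or effect size for this comparison. Its one power figure, 89% in Section 7.2.1, belongs to the primary comparison. It reproduces at 88.8% (Mann-Whitney, 40 vs 60, effect size 0.67) and has no bearing here.

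**Inputs.** From the documents: 100 evaluable patients split at the median, so about 50 per group; accrual up to 24 months (Section 7.2.2) and study length 48 months (Section 3.7), so follow-up of 48 − 24 = 24 to 48 months after PET. Assumed, because the documents give no value: median survival 18 months after PET, constant hazard, and exponential onset-to-PET delays with a mean of 12 to 24 months.

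**Step 1: the risk sets.** Let D be the delay from onset to PET and R the survival after PET. As written, the risk set at time t since onset holds everyone with D + R ≥ t. It should hold only those who have also entered before t.

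**Step 2: the median.** With a = 1/(mean delay) and b = ln 2/18 = 0.0385, the onset-clock survival curve of enrolled patients is S(t) = (a·e^(−bt) − b·e^(−at))/(a − b).
- Mean delay 12, t = 31: (0.0833 × 0.3031 − 0.0385 × 0.0755)/0.0448 ≈ 0.50.
- Mean delay 24, t = 42: (0.041667 × 0.19843 − 0.038508 × 0.17377)/0.003159 ≈ 0.50.

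The median reads about 31 or 42 months instead of 18.

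**Step 3: the comparison.** Simulated log-rank test, 2,000 replicates per cell; HR is high vs low heterogeneity.

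| Mean delay, low vs high (months) | True HR | Onset clock: HR, rejection | PET clock: HR, rejection |
|---|---|---|---|
| 12 vs 12 or 24 vs 24 | 1.0 | about 1, 5% | about 1, 5% |
| 12 vs 12 | 1.5 | about 1.4, 33% | about 1.5, 44% |
| 24 vs 24 | 1.5 | about 1.3, 25% | about 1.5, 44% |
| 12 vs 18 | 1.0 | about 0.78, 16% | about 1, 4–6% |
| 12 vs 24 | 1.0 | about 0.64, 45% | about 1, 4–6% |
| 24 vs 12 | 1.0 | about 1.56, 44% | about 1, 4–6% |

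A separate set of 1,500 replicates with gamma delays and a true HR of 1.8 shows reversal: delays of 12 vs 24 months give an onset-clock HR of 0.91.

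**Step 4: the gap between PET and enrolment.** In A1 it is up to 12 weeks. In A2 the PET may be 12 weeks before therapy, and enrolment must precede the on-treatment scan. By Section 5.3.6 that scan is due by week 12 + 4 = 16 (radioligand, chemotherapy, immunotherapy) or 20 + 4 = 24 (AR-targeted therapy). The A2 gap is therefore up to 12 + 16 = 28 or 12 + 24 = 36 weeks. In months the three gaps are 2.8, 6.4 and 8.3. The share dying within a gap is 1 − 2^(−gap/18), which gives 10%, 22% and 27%. With A2 gaps uniform up to 28 or 36 weeks, a plain PET clock reads a median of 19.2 or 19.8 months if half the patients are A2, and 21.0 or 21.7 if all are. Delayed entry returns 17.9–18.3.

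**Step 5: which clock drives the hazard.** The good PET-clock results in Step 3 use a constant hazard. With no true effect, delays of 12 vs 24 months and Weibull shapes 0.75 to 2:
- Hazard depends on time since onset: the onset clock with delayed entry gives HR 0.96–1.01 (rejection 4–7%). The unadjusted PET clock gives 0.89–1.38, with rejection up to 24%.
- Hazard depends on time since PET: the onset clock with delayed entry alone gives 0.74–1.06 (5–24%). Adding time since onset as a covariate brings it to 0.99–1.00 (5–7%).

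The covariate therefore matters. The PET clock with the covariate was not simulated for a hazard driven by time since onset, so its protection there is expected rather than measured.

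**The case against.** - **The analysis is exploratory.** It has no stated power, and Section 7.4.3 disclaims multiplicity adjustment. This stands and limits the weight of the point.
- **Nothing shows that delays differ between the groups.** This also stands. A reader might infer that the onset clock inflates false positives by itself. It does not: with equal delays type I error stays at 5%. The 45% figure needs one group's mean delay to be twice the other's, and the documents give no delay data. What remains under equal delays is inflated medians, dilution and lost power.
- **Onset of mCRPC is a legitimate origin.** It is, provided that risk sets open at entry. A reader might infer that delayed entry on this clock works only under a constant hazard. Step 5 shows otherwise: it is valid for any hazard shape in time since onset, if entry time is otherwise unrelated to survival. The documents do not say which clock drives the hazard.
- **The baseline-PET clock is not clean either.** True, because of the gap in Step 4 and because the analysis set is not fixed. Section 7.4.1 refers to subjects dosed in the study, and Section 3.2 makes patients without paired scans unevaluable for the primary analysis. If either rule governs this comparison, survival is guaranteed up to the relevant scan. The fix has to cover this.
- **The SUVmax range grows with lesion count.** The expected range is 1.13 SD for 2 lesions and 3.47 SD for 15 of identical variability. A reader might infer that lesion count must enter the main model. The documents do not establish that count is prognostic here, and this is a matter of the metric, not of the time origin.

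**Conclusion.** The plan is wrong as written for exploratory objective 3 and should be changed before analysis. An onset clock without delayed entry counts guaranteed survival as observed survival. On the assumed inputs, equal delays of 12 or 24 months move the median from 18 to about 31 or 42 months, reduce HR 1.5 to about 1.4 or 1.3, and cut power from about 44% to about 33% or 25%. Unequal delays of 12 vs 18 or 12 vs 24 months with no true effect give an HR of about 0.78 or 0.64 and rejection of about 16% or 45%.

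The mechanism follows from the text. The sizes rest on an assumed median, assumed delays and, in the unequal cases, an assumed link between delay and heterogeneity, so neither the size nor the direction of bias in this trial is known. The problem does not extend to the primary endpoint, the sample size or the secondary survival objective, whose time frame starts at baseline.

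**What to change.** 1. Count survival from the baseline PET, in line with the Section 2.3 time frame.
2. State the analysis set, and open each risk set at the later of baseline PET and enrolment. If inclusion requires a study dose, open it at the first on-study scan; if it requires paired scans, at the follow-up PET.
3. Name the model: Cox regression with delayed entry and time since mCRPC onset as a covariate.
4. Alternatively, keep the onset clock with left-truncated risk sets at that same entry time. Adding time since onset as a covariate protects against a hazard that depends on time since PET.
5. Optionally, adjust for lesion count, or use a spread measure less dependent on it, as a sensitivity analysis only.

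**Cost.** Analysis wording only: the plan already needs the onset, PET and enrolment dates. The time-since-onset covariate costs 0–4 points of power on the PET clock at HR 1.5 (41–44% versus 44–45%). Adjusting for lesion count would cost about 10–12 points at HR 1.5 (44% to 32%, or 43% to 33%) if counts are uniform over 1–15, which is why it is kept out of the main model.

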1.4 Rationale for Inclusion of Optional Paired Tumor Biopsy and FDG-PET

Whereas PSMA is uniformly expressed in the early prostate cancer, variable levels of PSMA expression have been reported in patients with castration-resistant disease.²¹ PSMA expression is inversely related to neuroendocrine biomarker genes,²¹ and treatment-emergent small-cell neuroendocrine prostate cancer (SCNC) may present as a low-uptake lesion on PSMA-based imaging.²² Additionally, up to 25% of patients screened for enrollment in PSMA-targeted radioligand therapy fail to meet inclusion criteria due to low- or heterogeneous-PSMA expression.^{11,12,23} “Discordant” metastases on serial Ga-PSMA- and FDG-PET imaging, with low PSMA and high Fluorodeoxyglucose (FDG) uptake, have also been described. Limited existing data on this subset of patients suggests a particularly aggressive cancer phenotype,²³ however the histologic and genomic features of this disease entity have yet to be defined. Furthermore, heterogeneous treatment effect and/or prior localized therapy may also contribute to intra-patient variations in PSMA expression. To address this and to better differentiate treatment-related PSMA suppression from discordant disease, we will offer an optional FDG-PET scan to patients with low- or heterogeneous PSMA uptake.²⁴ Additionally, we will offer optional paired tumor biopsies in selected patients with low PSMA expression, or heterogeneous PSMA uptake on Ga-PSMA PET imaging. As the use of Ga-PSMA PET imaging in mCRPC increases, there is an urgent need to better characterize these different patterns of PSMA expression. By quantifying variations in PSMA expression levels in patients with mCRPC, Ga-PSMA PET may offer non-invasive molecular insight into the underlying biology of advanced prostate cancer.

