5.3.2 Baseline ^{68}Ga -PSMA-11 PET/MRI or PET/CT

- ^{68}Ga -PSMA-11 PET/CT or PET/MRI
 - Participants will begin PET imaging between 55 and 70 minutes after the injection of Ga-PSMA-11 at a dose of 3-7 mCi.
 - A dose of 20 mg of furosemide (Lasix) is recommended to be injected intravenously together with, shortly before, or after, administration of the radiotracer in order to minimize PET scatter artifacts from excreted radiotracer accumulation in the kidney and urinary bladder that can occur with the gallium-68 radionuclide. Furosemide should not be administered in patients with medical contraindications to Furosemide.
 - Contrast agent for MRI or CT will be administered as clinically indicated.
 - Participants will be monitored for adverse events for two hours after Ga-PSMA-11 administration.
 - A formal radiology report from the imaging scan will be generated by the Nuclear Medicine department. If any unexpected findings are visualized, these will be reported to the treating health care provider, who will then contact the patient if additional work-up needs to be performed.
 - If the patient has received a ^{68}Ga -PSMA-11 PET scan prior to study enrollment and within 12 weeks prior to the start of current systemic therapy (sub-cohort A2), the PET scan may serve as the baseline PET scan and does not need to be repeated at screening.

5.3.3 Baseline Tumor Biopsy and Circulating Tumor Nucleic Acid Collection (Optional – Within 12 weeks of Baseline PSMA PET)

Patients in sub-cohort A1 will undergo optional metastatic tumor biopsy and circulating tumor nucleic acid collection within 12 weeks of baseline PSMA PET scan. Biopsy and/or circulating nucleic acid collection will be performed under protocol CC # 155518. Soft tissue lesions with low/negative PSMA uptake will be prioritized for tissue acquisition. However, either bone or soft tissue lesions that are deemed safely accessible per Interventional Radiology assessment will be potentially considered for imaging.

Optional circulating tumor nucleic acid collection under companion protocol CC# 155518 will also be performed at the following times:

- Initiation of systemic treatment
- Disease progression

5.3.4 Baseline FDG PET (Optional for sub-cohort A1 only – within 12 weeks of Baseline PSMA PET)

Patients in sub-cohort A1 may undergo optional FDG PET/CT scan (within 12 weeks after date of baseline Ga-PSMA PET) per standard imaging procedures.

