7.1 Imaging Analysis

A trained nuclear medicine physician will evaluate the reconstructed PET, CT or MRI, and fused PET/CT or PET/MR images using a PET volume computer-assisted reading software package. A positive lesion on PET will be defined as a focus of activity with higher SUV compared with mediastinal blood pool that is not attributable to other etiologies of tracer distribution (e.g. inflammation, excretion). A volume of interest (VOI) will be semi-automatically placed around each lesion, and the calculated maximum standard uptake value (SUV_{max}) will be recorded for each lesion, including lesions that are detected on standard scans but are not positive on PET. Adjusted SUV_{max} data will then be averaged the primary tumor and 5 largest lesions in each of three metastatic site (nodal, visceral, and osseous) within a given patient, up to a maximum of 16 lesions per patient ($SUV_{max-avg}$). Irradiated lesions will be excluded from this analysis.

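### Minor (exploratory): objective 2 concerns the per-patient SUVmax-ave, but section 7.4.3 plans only a per-lesion Pearson r between PSMA and FDG uptake, with no patient-level analysis and no handling of lesions within patients

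*Combined protocol and SAP*

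**What the plan says.** - Section 2.4, exploratory objective 2 (repeated in the Abstract), is to describe the relation of SUVmax-ave "on baseline Ga-PSMA PET with optional baseline FDG-PET".
- Section 7.1 defines SUVmax-ave as an average of lesion SUVmax "within a given patient, up to a maximum of 16 lesions per patient". It is therefore one number per patient.
- Section 7.4.3 gives the only PSMA/FDG analysis. It relates lesion SUVmax on the two scans, and the work "will be performed on a per-lesion basis amongst the subset of patients who have paired evaluable imaging using Pearson r correlation coefficient". It mentions no patient-level analysis, patient term, transformation or rank method.
- Section 7.4.3 also defines PSMA negative, low, intermediate and high lesions. It uses these categories for tissue features and does not cross them with FDG uptake.
- Section 1.4 gives the purpose of the scan, which is to separate treatment-related PSMA suppression from discordant (low-PSMA, high-FDG) disease. It states: "we will offer an optional FDG-PET scan to patients with low- or heterogeneous PSMA uptake".
- Section 5.3.4 describes the offer more broadly: "Patients in sub-cohort A1 may undergo optional FDG PET/CT scan". The expected number of FDG scans is not given.

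**The concern.** The objective and its analysis use different units. If 7.4.3 is followed exactly, SUVmax-ave is never related to FDG uptake, and objective 2 lacks the analysis that its wording calls for.

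The lesion-level analysis is reasonable in itself, since discordance is a property of lesions, but it is underspecified. A correlation over lesions from many patients combines two relations: whether patients with higher PSMA uptake have higher FDG uptake, and whether, inside a patient, the lesions with less PSMA have more FDG. These can differ in size or sign, and a single coefficient cannot separate them. SUVmax is positive and usually right-skewed, so Pearson r on the raw scale also gives the hottest lesions heavy weight.

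What is at stake is the interpretation of one descriptive result. A pooled r near zero could be read as no relation when low-PSMA/high-FDG lesions are present.

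**Working it through.** **Plan's own figure.** There is none to reproduce. The documents give no expected correlation, lesion variance split, number of FDG patients or precision for this analysis. The power statement in 7.2.1 concerns the primary endpoint only. All inputs below except the cap of 16 lesions are assumptions.

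**Step 1: match of units (no assumption needed).** Objective 2: SUVmax-ave, one value per patient (2.4, 7.1). Analysis: SUVmax, one value per lesion (7.4.3). No other sentence in 7.4.3 relates PSMA to FDG uptake. The mismatch is textual.

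**Step 2: what a pooled lesion-level r estimates.** Let s be the share of variance lying between patients, taken as equal for both tracers, on the log scale with equal lesion counts. Then

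pooled r = s × r_between + (1 − s) × r_within.

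With r_between = +0.5 and r_within = −0.5:

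| s | Formula | Simulated pooled r | Simulated within-patient r |
|---|---|---|---|
| 0.3 | 0.15 − 0.35 = −0.20 | −0.21 | −0.50 |
| 0.5 | 0.25 − 0.25 = 0.00 | −0.02 | −0.50 |
| 0.7 | 0.35 − 0.15 = +0.20 | +0.18 | −0.50 |

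The simulation used 30 patients with 2 to 16 lesions each and 600 data sets per row. The sign of the pooled value depends on s, while the within-patient estimate does not move.

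Milder case: r_between = 0, r_within = −0.4, s = 0.5 gives 0.5 × 0 + 0.5 × (−0.4) = −0.20 (simulated −0.21).

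Equal case: r = −0.5 at both levels gives s × (−0.5) + (1 − s) × (−0.5) = −0.50 for any s (simulated −0.49 to −0.50). Pooling then costs nothing.

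**Step 3: skew.** For lognormal variables with log-scale correlation r and log SDs a and b,

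raw Pearson = (exp(r·a·b) − 1) / √[(exp(a²) − 1)(exp(b²) − 1)].

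- r = −0.5, a = 0.7, b = 0.5: (exp(−0.175) − 1) / √(0.632 × 0.284) = −0.161 / 0.424 = −0.38.
- r = −0.5, a = 1.0, b = 0.8: (exp(−0.40) − 1) / √(1.718 × 0.896) = −0.330 / 1.241 = −0.27.

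**Step 4: a discordant subset.** Assume lognormal SUVs. Concordant lesions have PSMA median 12, FDG median 4, log SDs 0.7 and 0.5, and log-scale r 0.3. Discordant lesions have PSMA median 2 and FDG median 9, with log SDs 0.3 and 0.4. Raw Pearson r is 0.27, 0.02, −0.12 and −0.20 with 0%, 10%, 20% and 30% discordant lesions. At 10% the Spearman value is also about zero (0.01), so a rank method alone does not reveal the subset. A count does.

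**Step 5: precision.** With no true correlation at either level, a nominal 5% test that treats lesions as independent rejects in about 9% to 50% of runs (20 to 50 patients, 5 to 16 lesions each, s from 0.3 to 0.7). The plan announces no test here, so this matters only if a p-value or interval is reported.

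**The case against.** The strongest reply is that this is a descriptive, exploratory aim in an optional subset, on which no decision, sample size, or primary or secondary endpoint depends. That stands, and it sets the severity.

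The opposite-sign example is chosen so that the two parts offset each other. No document supports opposite signs. Section 1.4 describes PSMA suppression in patients as well as in lesions, so the same sign at both levels is at least as plausible, and with equal correlations pooling is harmless on the log scale. This also stands: Step 2 shows what can happen and does not predict it.

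That the lesions are pooled into one coefficient on untransformed values is inferred from silence. Section 7.4.3 does not exclude per-patient coefficients, and 7.1 mentions an adjusted SUVmax without defining the adjustment. This is fair, but it is also a reason to specify the analysis.

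Two stronger readings are tempting, and the documents do not support them:

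- *Offering FDG to low-uptake patients shrinks r by range restriction.* Section 1.4 selects patients, not lesions, and names low or heterogeneous uptake. Heterogeneous patients contribute lesions across the range. For a true r of −0.5 at both levels and s = 0.5 (40,000 simulated patients, 2 to 16 lesions; low = lowest quarter or half of patient means; heterogeneous = highest half or quarter of within-patient ranges), such selection gives a pooled r of −0.49 to −0.53, so there is no meaningful shrinkage.
- *The coefficient answers no relevant question.* A per-lesion correlation does speak to lesions. The interest in discordance comes from the rationale in 1.4, not from objective 2, which asks only for a description of the relation.

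The difference between 1.4 and 5.3.4 may be no more than a narrow motivation beside a broader permission. It still leaves the scanned group undefined for the reader of the result.

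**Conclusion.** The point holds as a minor, exploratory one. The mismatch between SUVmax-ave in objective 2 and the per-lesion SUVmax analysis in 7.4.3 is plain from the text and needs no assumption. The absence of any stated handling of up to 16 lesions per patient is equally plain.

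The size of any distortion cannot be known from the documents. It ranges from nothing on the log scale (equal correlations at both levels) to a pooled r between about −0.21 and +0.18 against a within-patient −0.5 (between-patient +0.5, variance share 0.3 to 0.7). Skew can separately turn a log-scale −0.5 into −0.38 or −0.27 under the assumed log SDs. The primary result, the sample size and the power are untouched.

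**What to change.** Replace the PSMA/FDG sentence in 7.4.3 with:

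1. **Patient level, matching objective 2.** Spearman correlation of PSMA SUVmax-ave with FDG SUVmax averaged over the same lesions. The FDG average needs a definition, because 7.1 defines the average only for the PSMA reading.
2. **Lesion level.** On log SUVmax, the within-patient correlation (patient effects removed) next to the overall correlation, with confidence intervals from a bootstrap that resamples patients.
3. **Direct count.** The number of low- or negative-PSMA, FDG-avid lesions and the number of patients with at least one, using the PSMA categories already in 7.4.3 and a stated definition of FDG-avid. This is needed because removing patient effects discards the information from patients whose lesions are all PSMA-low and FDG-high.

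Reconcile 1.4 with 5.3.4 on who is offered FDG PET, and describe the scanned patients when reporting.

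Cost: protocol wording and a little more analysis. The scans and measurements are the same, and no participants are added.
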